#### **3.3 Sample and population**

The participant in this study will be recruited from the adult cardiac surgery division at the National Cardiovascular Centre Harapan Kita, Jakarta, Indonesia. All participants will be selected randomly and are eligible for cardiac surgery. Participants then will undergo an eligibility assessment based on the inclusion and exclusion criteria. Afterwards, the participants that are qualified for this study will be divided into two groups (control vs treatment group) randomly.

#### **3.4 Inclusion and exclusion criteria**

Inclusion Criteria:

1. Patients ages > 18 years old
2. Patients who are scheduled electively for cardiac surgery
3. Cardiac surgery with the usage of cardiopulmonary bypass machine
4. Patients who are agreed to participate in this study

Exclusion Criteria:

1. Patients who are scheduled for surgery in emergency or urgent manner
2. Patients with the history of uncontrolled hypertension and uncontrolled diabetes mellitus.
3. Patients with the history of past cardiac surgery

Drop – out Criteria:

1. Patients who are pronounced death on operation table
2. Patients who are pronounced death within hospitalization
3. Patients who are lost to follow up (Day 30 post-operative)
4. Patients who are not committed for the whole stage of the research

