**Specific Objectives:**

1. To compare the surgical site infection and sternal dehiscence rates at the end of hospital stay, day 14 post operation, and day 30 post operation in post cardiac surgery patient with the application of Sternum Guard™ as opposed to bone wax intraoperatively.
2. To compare the haemostasis effect of Sternum Guard™ as opposed to bone wax intraoperatively in cardiac surgery.
3. To compare the satisfaction rate (includes global satisfaction rate, haemostasis and dryness of surgical site, and mechanical protection) of the surgeons who are using the Sternum Guard™ as opposed to bone wax intraoperatively in cardiac surgery.

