### 3.7 Sample size estimation

The sample size in this study is estimated by using the formula for hypothesis tests for two population proportions (two-sided test)

$$n = \frac{\left\{ Z_{1-\alpha/2} \sqrt{2\bar{P}(1-\bar{P})} + Z_{1-\beta} \sqrt{P_1(1-P_1) + P_2(1-P_2)} \right\}^2}{(P_1 - P_2)^2}$$

details:

$\alpha$  : 5

$1-\beta$  : 90

$P_1$  : 0.15

$P_2$  : 0.05

$n$  : 376

From the equation above, it is estimated for the sample size of the study to be 376 samples, with estimated drop out proportion of 10%, it is deduced the sample size of 414 samples.

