### **3.9 Data analysis**

All collected data will be verified and will be statistically analyzed using SPSS and the result from the data analysis was considered statistically significant with a p-value of  $< 0.05$ . For descriptive analysis, we will perform the analysis independently for numerical and categorical data. All numerical data will be analyzed using Coefficient of Variance and confirmed by Kolmogorov-Smirnov normality test. Normally distributed data will be analyzed using mean and standard deviation, meanwhile the abnormally distributed data will be analyzed using median, minimum value and maximum value. Categorical data analysis will be presented by percentage and frequencies table.

For inferential data analysis, we will perform the comparison tests and mean comparison test. The proportion comparison tests are applied for comparing categorical independence variable between Sternum Guard™ and bone wax group, such as Chi-square test and Fisher's Exact test as an alternative for chi-squared test. Mean comparison tests are utilized for comparing numerical independence variable between Sternum Guard™ and bone wax group, such as Independent T-Test and Mann-Whitney test for the non-parametric test.

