### 3. 13 Research flow

### 3.14 Dummy table

#### Participant Characteristic

Table 2 - Dummy Table 1

	Sternum Guard™		Bone Wax	
	N	%	N	%
Age **				
Male *				
CABG *				
CABG + VALVE*				
VALVE *				
VASCULAR *				
Hypertension *				
Diabetes Mellitus *				
CPB time < 60 minutes *				
CPB time > 60 minutes *				

\*) n(%)

\*\* ) mean + SD

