#### Outcomes

Table 3 - Dummy Table 2

	Sternum Guard™		Bone Wax	
	N	%	N	%
Primary Outcomes				
Surgical Site Infection:				
Superficial *				
Deep *				
Sternal Dehiscence:				
Yes *				
No *				
Haemostasis Effect (gr)**				
Satisfaction Rates **				
Satisfied				
Fairly satisfied				
Fairly dissatisfied				
Dissatisfied				

\*) n(%)

\*\* ) mean + SD

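### Section 3.4 makes in-theatre death, in-hospital death, loss at day 30 and lack of commitment drop-out criteria, but no readable section defines an analysis set or says what happens to drop-outs or to their recorded events

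*Combined protocol and SAP*

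**What the plan says.** Section 3.4 gives the drop-out criteria separately from the inclusion and exclusion criteria. They are death on the operating table, "Patients who are pronounced death within hospitalization", "Patients who are lost to follow up (Day 30 post-operative" at the last scheduled visit, and "Patients who are not committed for the whole stage of the research". The last has no operational definition. Death after discharge but before day 30 is not listed.

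Section 3.7 computes 376 and then continues "with estimated drop out proportion of 10%, it is deduced the sample size of 414 samples".

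Section 3.9 opens with "All collected data will be verified and will be statistically analyzed using SPSS" and goes on to descriptive summaries and tests (chi-square or Fisher's exact, t-test or Mann-Whitney). It names no analysis set and gives no rule for deaths, missed visits, or events seen before drop-out. Sections 3.5, 3.6, 3.10 and 3.11 give none either.

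Objective 1 in Section 1.5 compares SSI and "sternal dehiscence rates at the end of hospital stay, day 14 post operation, and day 30 post operation". The outcome shell, "Table 3 - Dummy Table 2", lists superficial SSI, deep SSI and dehiscence separately, with no time points and no stated denominator. The figure under "3. 13 Research flow" cannot be read in the copy available, so it is not counted for or against the plan.

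**The concern.** The four criteria define a class of patients called drop-outs, and the sample is enlarged so that 376 remain for the powered comparison. Read together, Sections 3.4 and 3.7 point to an analysis of those who complete day 30.

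Such a comparison is no longer between the groups as randomised, and removal can depend on the outcome being measured. A patient with an SSI recorded at discharge who misses day 30 meets a drop-out criterion. So does a patient who dies in hospital of a deep infection. Section 2.6 itself cites 19 to 29% mortality with deep sternal infection, and Section 2.7 calls dehiscence a surgical emergency.

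The direction of bias cannot be predicted. Dropping a fatal infection removes an event; dropping a death on the table removes a patient who had no chance to show one. If exclusion is not intended, the handling is still open and could be settled after the data are seen.

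**Working it through.** **Inputs.** From Section 3.7: two-sided 5% level, 90% power, P1 = 0.15, P2 = 0.05, 376 before and 414 after the drop-out allowance. From Table 6: 207 Sternum Guard pieces, which fits 414/2 and equal allocation. From Section 2.6: deep infection incidence 1.8% (registry), range 0.8 to 5.0%; mortality 19 to 29%.

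**Assumptions.** The two proportions are the arm event rates (Section 3.7 does not label them), and the cited mortality falls within the hospital stay (Section 2.6 gives no time window).

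**1. The plan's own figure.** The Section 3.7 formula, per arm, is {1.960·√(2·0.10·0.90) + 1.282·√(0.15·0.85 + 0.05·0.95)}² / 0.10² = 187.05, so 188 per arm and 376 in total. This reproduces exactly. Then 376 × 1.10 = 413.6, so 414, or 207 per arm. Solving the same formula for power gives 90.1% at 188 per arm and 92.7% at 207.

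**2. The drop-out allowance.** (414 − 376)/2 = 19 per arm. This covers all four criteria together; no split is given. If drop-out is unrelated to outcome, 19 × 0.15 = 2.85 and 19 × 0.05 = 0.95 events would fall among these patients. The documents do not show how many would be recorded before drop-out.

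**3. Removing fatal deep infections.** Let f = incidence × mortality. The number per arm of 207 is 207f. Removing a fraction g of an arm, all of them events, changes its rate from p to (p − g)/(1 − g). Power is at 188 per arm. Three patterns by arm were tried: f from the 15% arm only; f from the 15% arm and f/3 from the 5% arm (in proportion to events); f from each arm.

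| Incidence, mortality | 207f | 15% arm only | In proportion | f from each arm |
|---|---|---|---|---|
| 1.8%, 19% | 0.71 | 88.8% | 89.6% | 91.1% |
| 1.8%, 29% | 1.08 | 88.0% | 89.3% | 91.6% |
| 5.0%, 29% | 3.00 | 83.2% | 87.6% | 94.1% |

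For example, in the last row f = 0.05 × 0.29 = 0.0145 and (0.15 − 0.0145)/(1 − 0.0145) = 0.1375. The 5% arm becomes 0.0500, 0.0454 or 0.0360 under the three patterns. Equal removal raises power because it takes a larger share of the events in the low-rate arm.

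**4. How far the handling could matter (assumed counts, not predictions).** Take 21 drop-outs per arm (10% of 207) and completers at 28/186 versus 9/186: chi-square p = 0.001. Count all 207 per arm:
- no events among drop-outs: 28/207 versus 9/207, p = 0.001;
- 0 and 10 events among drop-outs: 28/207 versus 19/207 (13.5% versus 9.2%), p = 0.16.

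**5. Cost of counting everyone.** If 19 per arm are lost and none of their events were recorded, the rates become 0.15 × 188/207 = 13.6% and 0.05 × 188/207 = 4.5%, a difference of 9.1 points, with power 89.8% at 207 per arm. If all their events were recorded first, the rates stay at 15% and 5% and power is 92.7%.

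**The case against.** The plan never says that drop-outs are removed from analysis. A 10% inflation is routine and fits either reading. Section 3.9 refers to all collected data, and Objective 1 compares rates at three times, so a patient lost at day 30 could still count at discharge and day 14. The research-flow figure might say more. All of this stands, so a reader who concludes that the plan prescribes a completers-only analysis goes beyond the text. What is established is that the analysis set is undefined. None of these points defines it: the Section 3.9 phrase concerns verification and software, and the outcome shell does not say which visit or denominator applies.

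Four other inferences are tempting and unsupported:
- **That power is eroded.** The table shows movement in both directions.
- **That loss to follow-up is the main group.** The 19 per arm is for all four criteria.
- **That every death is a drop-out.** Only in-theatre and in-hospital deaths are listed.
- **That a fatal infection would usually have been logged at a scheduled post-operative check.** An in-hospital death precedes discharge, so apart from day 0 this holds only for patients still in hospital at day 14.

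The cited extremes may also not apply to the elective, first-operation population of Section 3.4.

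**Conclusion.** The point holds as an undefined analysis set, with completers-only as the natural but unstated reading. Confidence is high on the missing definition and lower on what the authors intend. The main risk is bias of unknown direction, plus freedom to choose the handling late; it is not loss of power. Against 90.1% planned, removing fatal deep infections gives about 88 to 92% at the registry incidence and about 83 to 94% at the cited extremes, depending on how losses fall by arm. These figures rest on the unlabelled proportions being the arm rates and on the cited mortality being in-hospital. The matter should be corrected before analysis, but it does not undermine the design.

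**What to change.** - **Section 3.4:** keep the four criteria only as reasons for ending follow-up, and say that they do not remove a patient from analysis.
- **Section 3.9:** make the primary comparison all randomised patients by allocated arm, separately for superficial SSI, deep SSI and sternal dehiscence as the outcome shell lists them. Count any event recorded by day 30, up to death or last contact; this also covers death after discharge. Do not merge SSI and dehiscence into a composite, which the shell does not state. Analyse haemostasis and satisfaction in all randomised patients with data.
- **Section 3.14:** report deaths and drop-outs by arm and reason.
- **Sensitivity analysis:** for patients with no recorded event and unknown day-30 status, including deaths, vary the assumed number of events separately by arm and report where the conclusion changes.

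The cost is wording, some table rows and one analysis; no extra patients. Two downsides should be stated in the plan. Event-free losses count as non-events, which dilutes the difference to 9.1 points in the worst case of step 5, with power 89.8%. Infection status for patients who die before a scheduled wound check may have to come from hospital records written by staff who know the allocation, whereas Section 3.5 has the project leader assess the data blinded.

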### **3.5 Randomization and blinding procedure, and assessment schedule**

Participants which are included in this study will be randomized into two groups: A. Control Group (Bone Wax) and B. Treatment Group (Sternum Guard™). The randomization process will be conducted by a *block randomisation technique*. This study is conducted in a single blind manner. The surgeons will not be blinded by the intervention, as it is impossible for the surgeons to not acknowledge the intervention. The participants on both groups will be blinded for the intervention given. The project leader will also be blinded when gathering and assessing the data from the study. Both of the groups then will be assessed for outcomes intraoperatively, at the end of the hospital stay, day 14 post – operative, and day 30 post - operative. The surgeons' point of view on both interventions will be evaluated after the surgery.

### **3.6 Data extraction**

Every participant included in this study will be scheduled for any cardiac surgery electively. Every participant will undergo the surgery with cardiopulmonary bypass. All of the surgery will be conducted in a similar manner, however, if there is any complication intraoperatively, every action will be taken according to the situation and will be recorded. Before incision the Sternum Guard™ and sterile drapes for the bone wax group will be weighed. After median sternotomy, the surgeons will be given Bone Wax or Sternum Guard™ to be applied to the sternum. The decisions will be made based on the block randomisation technique and will be informed beforehand to the nurse scrub and the surgeon. In the Bone Wax group, cauterization will be used according to the sternum's condition and surgeon's decision before applying the sterile draping and after removing it if needed. In the Sternum Guard™ group, cauterization will also be applied before inserting it to the sternum and after removing the Sternum Guard™ if needed.

Subsequent to median sternotomy, sternal bleeding will be assessed. In the Sternum Guard™ group, immediately before cauterization and in Bone Wax group right before applying the bone wax.

Once the surgery is done, the Sternum Guard™ and the sterile drapes will be weighed again. Sternal trauma will be evaluated at the end of surgery (visible trauma or no visible trauma). In the Sternum Guard™ group, within 5 minutes of Sternum Guard and sternal retractors removal and on the Bone Wax group within 5 minutes of removal of the sterile drapes and sternal retractors. Another sternal bleeding assessment will be done on both groups. In the Sternum Guard™ group it will be assessed immediately after removing the Sternum Guard, before the cauterization, while on the Bone Wax group, before applying any bone wax and cauterization. The sternotomy wound will be evaluated and documented at Day 0, at the end of hospital stay, Day 14 post - operative, and Day 30 post-operative. After the surgery, the surgeons will be given questionnaire regarding the use of Sternum Guard™ as opposed to Bone Wax.

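### The surgeon may be told the arm before sternotomy, first cautery and first bleeding assessment, and nothing in the plan protects the block sequence from prediction

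*Combined protocol and SAP*

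**What the plan says.** Section 3.5 gives the blinding scheme. The trial is labelled single blind ("This study is conducted in a single blind manner"). Participants are blinded ("The participants on both groups will be blinded for the intervention given"), and so is the project leader ("The project leader will also be blinded when gathering and assessing the data from the study"). Surgeons are not: "The surgeons will not be blinded by the intervention, as it is impossible for the surgeons to not acknowledge the intervention". The only detail on randomisation is that it is done in blocks. The protocol gives no block size, does not say whether the size varies, and names neither a holder of the list nor a method of concealment.

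Section 3.6 sets out the theatre sequence and how the arm is communicated: the block-based decisions "will be informed beforehand to the nurse scrub and the surgeon". It does not say how long beforehand. In the same section:

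- the Sternum Guard, or the drapes used in the bone wax arm, are weighed before incision;
- the product is handed over after the sternotomy;
- cautery before the product is described separately for each arm, and in the bone wax arm it is left to the surgeon's judgement;
- the first sternal bleeding assessment comes just before cautery in the Sternum Guard arm, and just before the wax is applied in the bone wax arm.

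**The concern.** The reason given in section 3.5 for not blinding surgeons is that they cannot fail to recognise what they are using. That holds from the moment the product is in hand, but it does not cover the period before. If the surgeon already knows the arm, the sternotomy and the first cautery can be handled differently in the two groups, deliberately or not. Section 2.5 itself names an off-centre sternotomy and overuse of electrocautery among the technical risk factors for sternal infection or dehiscence. Cautery before the product may also change the blood later weighed as the haemostasis outcome, which Table 3 lists under primary outcomes. A difference produced in this way would be credited to the product, and analysis could remove it only in part.

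The second issue is distinct. With unblinded surgeons, past allocations are known to at least some theatre staff. Block randomisation with an unprotected block size can then let someone anticipate the next arm. If that person also influenced who is enrolled or in what order, the groups could differ at baseline.

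**Working it through.** **Part 1: order of events (no arithmetic applies).** Setting the steps of section 3.6 in time order:

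1. Arm communicated beforehand to scrub nurse and surgeon; exact time not given.
2. Arm-specific material weighed, before incision. Someone in theatre knows the arm by now.
3. Sternotomy.
4. First bleeding assessment and first cautery, both described by arm.
5. Product or drapes applied.

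Steps 3 and 4 do not require the surgeon to know the arm in order to use the product, but the text permits that knowledge. In the Sternum Guard arm the assessment at step 4 precedes cautery. In the bone wax arm it is tied to the wax, and cautery is allowed before draping, so the assessment may follow cautery. The two assessments may therefore not be made at comparable points, even with no bias from knowledge of the arm.

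**Part 2: how predictable blocks can be.** The plan states no figure on this. The only documented input is the planned total of 414 (section 3.7: 376 × 1.10 = 413.6, rounded up). Block size, its being fixed and known, 1:1 allocation within blocks and the number of surgeons are assumptions.

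*Someone who sees every earlier allocation.* Take blocks of 2b with b patients per arm. The share of allocations that are certain is 1/(b+1). The best-guess success rate is {b + [2^(2b)/C(2b,b) − 1]/2}/(2b).

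- Blocks of 4 (b = 2): certain 1/3. Success {2 + [16/6 − 1]/2}/4 = 2.833/4 = 70.8%.
- Blocks of 6 (b = 3): certain 1/4. Success {3 + [64/20 − 1]/2}/6 = 4.1/6 = 68.3%.

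Listing the six possible blocks of 4 confirms the first result. AABB and its mirror image give 2.5 expected correct guesses; the other four sequences give 3. The mean is (2 × 2.5 + 4 × 3)/6 = 2.833. Over 414 patients, the certain allocations number 414/3 = 138 (blocks of 4) or 414/4 = 103.5 (blocks of 6). Across block sizes of 2 to 10, success runs from 75.0% down to 65.3%, against 50% by chance.

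*A surgeon who sees only their own cases.* This was simulated with 400 runs of 414 patients and cases falling to surgeons at random. Each surgeon guesses the arm they have used less so far.

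| Surgeons | Blocks of 4 | Blocks of 6 |
|---|---|---|
| 2 | 51.9% | 51.7% |
| 4 | 50.9% | 51.0% |
| 8 | 50.7% | 50.5% |

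That rule ignores the patient's position in the block. A surgeon who knew it, for instance from study numbers, would do better. With blocks of 4, the best guess succeeds with probability 1/2, 2/3, 2/3 or 1 after seeing 0, 1, 2 or 3 earlier allocations of that block. With two surgeons, each sees half of the earlier cases on average. Success at positions 1 to 4 is then 0.500, 0.583, 0.625 and 0.6875, a mean of 2.396/4 = 59.9%.

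**The case against.** The strongest reply has five parts.

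- A reader might infer that telling the surgeon early is what makes later allocations guessable. It is not. Surgeons learn the arm on applying the product in any case, so later disclosure leaves past allocations just as visible. Guessability comes from blocks plus unblinded staff. This part of the reply stands, and the two issues must be kept apart.
- A reader might also infer that enrolment was, or will be, manipulated. The documents do not support this. Section 3.3 puts eligibility assessment before random division, and nothing says that surgeons or nurses enrol patients or set the order. The 71% and 68% figures are upper cases for someone who sees everything. The centre reported 1721 adult operations in 2017 (section 1.1) and the protocol speaks of surgeons in the plural, so one surgeon seeing every allocation should not be presumed. This stands.
- Calling the trial unblinded would be too broad, since participants and the project leader are stated to be blinded. This stands.
- The word beforehand may mean only before the product is handed over. This is a possible reading. But the wording does not limit disclosure to that moment, and the weighing means that the arm is known to someone in theatre before incision. The knowledge is permitted, not proven.
- The first bleeding assessment is not itself a listed outcome in section 3.10 or Table 3, section 3.6 does not say that the surgeon scores it, and cautery after product removal is unblinded regardless. This limits the harm from biased scoring. It does not answer the point about sternotomy and first cautery, which come before the product and bear on listed outcomes.

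**Conclusion.** The point holds in two separate parts. First, section 3.6 allows the surgeon to know the arm during steps that do not yet involve the product, and the reason given for leaving surgeons unblinded does not extend to that period. Infection, dehiscence and weighed blood loss could all be affected. The documents give no basis for estimating by how much. Second, the plan has no protection against prediction of later allocations. Success could be 71% (blocks of 4) or 68% (blocks of 6) if blocks are fixed and known and every allocation is seen. It is about 50.5% to 52% for one of 2 to 8 surgeons who tracks only their own running balance, and about 60% for one of two surgeons who also knows the position in a block of 4. All of these rest on assumed block sizes and surgeon numbers. They describe a risk left open, not a bias shown to exist, because who enrols is not stated. The sample size is unaffected. The change is a cheap improvement worth making.

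**What to change.** In section 3.6, replace the sentence on advance notice. State that the allocation is opened by theatre staff other than the surgeon, only once the patient is enrolled and in theatre. The surgeon is told only after the first sternal bleeding assessment. Two further changes are needed for this to work:

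- Arrange the weighing before incision so that it does not reveal the arm to the surgeon, for example out of the surgeon's sight.
- Set the first bleeding assessment at the same point in both arms. Reconcile the arm-specific descriptions of the steps before the product, including cautery, with that common point. How cautery is used remains a clinical matter for the investigators.

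In section 3.5, specify randomly varied block sizes that are not disclosed to surgeons or nurses, and a list held by someone outside both enrolment and theatre. Add who enrols patients.

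The cost is rewording two sections, generating a new list and slightly tighter theatre logistics. Surgeons will still know the arm once they use the product, so this shortens the unblinded period without removing it.
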